2.3. Study Design

Overview of Study Design and Key Features	
Dosing	
 Participants will receive oral study treatment (gepotidacin [2 tablets] + nitrofurantoin matching placebo [1 capsule] or nitrofurantoin [1 capsule] + gepotidacin matching placebo [2 tablets]) BID (approximately every 12 hours) for 5 days. The first oral dose will be administered at the study site during the Baseline Visit; participants will self-administer subsequent doses as outpatients thereafter, beginning with the second dose, with the exception of 1 dose at the OT Visit that will be taken at the study site whenever possible.
Time & Events	
 Refer to Appendix 1
Treatment Assignment	
 Participants will be stratified, as described in Figure 1, and will be randomly assigned in a 1:1 ratio to receive one of the following study treatments: 
 Gepotidacin: 1500 mg administered orally twice daily (BID) for 5 days Nitrofurantoin: 100 mg administered orally BID for 5 days
Interim Analysis	
 One interim analysis will be planned to assess fertility and efficacy or fertility only. An independent data monitoring committee (IDMC) will review unblinded data to make recommendations to GSK. Details regarding the IDMC process will be available in relevant IDMC documents.

2.4. Statistical Hypotheses / Statistical Analyses

The study is designed to determine whether gepotidacin administered orally is noninferior compared with nitrofurantoin administered orally on the primary efficacy endpoint of therapeutic response (combined per-participant microbiological and clinical response) at the TOC Visit in participants with a qualifying uropathogen at Baseline that is susceptible to nitrofurantoin. Microbiological success per-participant is defined as eradication (i.e., reduction of all qualifying uropathogens recovered at Baseline to $<10^3$ CFU/mL as observed on quantitative urine culture) without the participant receiving other systemic antimicrobials prior to the urine culture assessment conducted at the TOC Visit (evaluated at the resolution of minutes). Clinical success is defined as resolution of all signs and symptoms of acute cystitis present at Baseline (and no new signs and symptoms) without the participant receiving other systemic antimicrobials. For systemic antimicrobials received for the current infection (as rescue treatment) prior to or on the TOC Visit will be considered a clinical failure. For systemic antimicrobials received for other infection (as non-rescue treatment) prior to the TOC Visit will be considered a clinical failure.

The following are null and alternative hypotheses for the primary analysis of the therapeutic success rates at the prespecified noninferiority margin of -10.0%:

H_0 : therapeutic success rate of Gepotidacin 1500 mg BID – therapeutic success rate of Nitrofurantoin 100 mg BID \leq -10.0%

H_1 : therapeutic success rate of Gepotidacin 1500 mg BID – therapeutic success rate of Nitrofurantoin 100 mg BID $>$ -10.0%

At the interim, if the Z statistic (for the primary analysis population) is higher than the Z statistic boundary for noninferiority, noninferiority will be tested in a supplementary analysis population (micro-ITT NTF-S (IA Set) (CAPA)) to ensure consistency. If the Z statistic (for the supplementary analysis population) is also higher than the Z statistic

boundary for noninferiority the study will be stopped for efficacy and noninferiority will be declared.

Note: The stopping boundaries for this key supplementary analysis will be consistent with the primary analysis (as will the null and alternative hypotheses), the futility bounds will be presented for reference only (and not to be used as formal futility hypothesis testing).

At the final analysis (if the study continues at the IA), if the Z statistic (for the primary analysis population) is higher than the Z statistic boundary for noninferiority the study will be declared successful and noninferiority will be declared. Refer to Section 5.5 for further details on study success definition and IA recommendation framework.

If noninferiority is declared between gepotidacin and nitrofurantoin, superiority will be tested in the primary analysis population with the following null and alternative hypotheses:

H₀: therapeutic success rate of gepotidacin 1500 mg BID – therapeutic success rate of nitrofurantoin 100 mg BID $\leq 0\%$

H₁: therapeutic success rate of gepotidacin 1500 mg BID – therapeutic success rate of nitrofurantoin 100 mg BID $> 0\%$

If the one-sided p-value is less than the p-value boundary superiority of gepotidacin will be declared.

The difference in therapeutic success rates between the two study treatment groups and its Z statistic use the Miettinen-Nurminen (MN) method (Miettinen, 1985) stratified by age category (≤ 50 years, or > 50 years) and acute cystitis recurrence (nonrecurrent infection or recurrent infection) combinations. In the event that any participants are misstratified, for the primary efficacy analysis, the actual age and acute cystitis collected in eCRF will be used to create actual pooled stratification. A sensitivity analysis of the primary efficacy analysis will also be conducted from the pooled stratification as randomized.

3. PLANNED ANALYSES

3.1. Interim Analyses

One IA is planned to assess either both efficacy (noninferiority) and futility or just futility by the IDMC. The IDMC will meet when approximately 60% of participants in the micro-ITT NTF-S Population have achieved the TOC Visit to evaluate the primary endpoint, identify potential treatment benefit, and make recommendations for continuing or stopping the study, as per the IDMC charter. The scope of data for the IA reporting will include (a) participants who had the opportunity to reach their Test of Cure (TOC) visit and (b) participants who have not yet reached their TOC visit, but are already known to be failures (e.g., subjects who took other systemic antimicrobial or withdrew from the study before the TOC visit). The IDMC members will include at least 3 independent experts (from a total of 5 planned), including an infectious disease specialist, a

chairperson with experience chairing IDMC meetings, and a statistician. Details regarding the IDMC process will be described in the IDMC charter.

The Statistical Data Analysis Centre (SDAC), a PPD unblinded statistical team, will conduct and provide all unblinded analyses to the IDMC before the meeting is held. The GSK and PPD study teams that are operating the study and conducting the final analysis will remain blinded. The IDMC and SDAC will maintain unblinded data in a secure area to ensure the integrity of the data until the study is completed. Details on protecting blind and data integrity will be described in a blinding plan.

At the time the IA is conducted, the IDMC will review unblinded data to confirm that sufficient microbiological data exist for the unblinded gepotidacin treatment arm before deciding how to proceed as detailed in the IA RAP.

If the IDMC confirms there is sufficient microbiology data in the gepotidacin arm, an IA with stopping rules for both efficacy and futility will be performed. The nominal significance levels for the interim and final analyses will be determined by the Lan-DeMets spending functions approach [Lan, 1983]. This will be based on the Pocock stopping boundary for efficacy and the O'Brien-Fleming stopping boundary for futility. The futility bounds of this study are nonbinding and are considered guidance rather than strict bounds. The IA recommendation framework requires both the primary and supplementary analyses to meet the NI boundary to stop the study for efficacy at the interim analysis as described in Section 5.5. For futility, only the micro-ITT NTF-S population will be used to determine if the futility boundary has been met (i.e., not the micro-ITT NTF-S (CAPA) population).

During the course of the IA, patients will continue to be randomized. If efficacy success (i.e., noninferiority) is reached at the IA and the study is stopped early, the IA efficacy results will be the primary analysis to support the effectiveness of the study. If efficacy success is not reached at the IA, the study will continue to the maximum target sample size for the micro-ITT NTF-S Population of approximately 884 participants.

If, at the IA, the IDMC confirms that there is not sufficient microbiology data in the gepotidacin arm, then a futility-only IA will be conducted. The nominal significance levels for the interim and final analyses will be determined by the Lan-DeMets spending functions approach [Lan, 1983]. This will be based on the O'Brien-Fleming stopping boundary for futility. The futility bounds of this study are nonbinding and are considered guidance rather than strict bounds. Note: only the micro-ITT NTF-S population will be used to determine if the futility boundary has been met (i.e., not the micro-ITT NTF-S (CAPA) population). The stopping boundaries will be calculated under the assumption of an approximate maximum sample size of 768 participants in the micro-ITT NTF-S Population, a 76% therapeutic success rate for nitrofurantoin, a -10.0% noninferiority margin and a 0.025 one-sided alpha level. If the decision is to continue at IA, the boundary for final analyses will not be updated as it is based on the planned sample size.

Table 2 summarizes the information fraction, sample size and decision guidance (boundaries in Z-statistics and *p*-value, cumulative alpha, and beta) for the planned IA at 60% timing (i.e., a planned end of study sample size of 884 participants in the micro-ITT NTF-S Population) with a -10.0% noninferiority margin, 0.025 one-sided type I error and

a 0.1 type II error approximately and assuming a 76% therapeutic success rate for nitrofurantoin. If the decision is to continue at IA, the boundary for final analyses will not be updated as it is based on the planned sample size of 884.

Table 2 Information Fraction and Stopping Boundaries for Efficacy and Futility IA

Information Fraction	Target Sample Size for each study	Efficacy Boundary			Non-Binding Futility Boundary		
		Z statistics	p-value	Cumulative alpha	Z statistics	p-value	Cumulative beta
60%	530	>2.104	<0.018	0.018	<0.854	>0.197	0.033
100%	884	>2.23	<0.013	0.025	<2.23	>0.013	0.098

Information fraction is determined using CLSI based micro-ITT NTF-S. Testing for noninferiority and superiority share the same Z statistics and p-value boundaries.

[Table 3](#) summarizes the information fraction, sample size, and decision guidance (boundaries in Z-statistics and p-values, cumulative beta) for the planned IA for futility only. The IA will occur at 530 participants and this corresponds to 69% information fraction for futility-only IA (i.e., a planned end of study sample size of 768 participants in the micro-ITT NTF-S Population) with a -10.0% noninferiority margin, 0.025 one-sided type I error and assuming a 76% therapeutic success rate for nitrofurantoin. The actual boundaries will be determined based on the actual information fraction in the micro-ITT NTF-S (IA Set) population at the time of IA. If the decision is to continue at IA, the boundary for final analyses will not be updated as it is based on the planned sample size of 768. Boundaries are calculated in software EAST using Wald statistics without adjusting for strata.

Table 3 Information Fraction and Stopping Boundaries for Futility Only IA

Information Fraction	Target Sample Size for each study	Non-Binding Futility Boundary		
		Z statistics	p-value	Cumulative beta
69%	530	<1.128	>0.13	0.059
100%	768	<1.96	>0.025	0.116

Information fraction is determined using CLSI based micro-ITT NTF-S

The efficacy boundaries and non-binding futility boundaries in [Table 2](#) and [Table 3](#) are based on initially assigned information fraction and are calculated in software EAST using Wald statistics without adjusting for strata. The actual boundaries will be determined based on the actual information fraction in the micro-ITT NTF-S (IA Set) population at the time of IA. If the decision is to continue at IA, the boundary for end of study analyses will not be updated as it is based on the planned sample size.

Sensitivity analyses (i.e., unadjusted treatment difference and treatment difference adjusting for strata as randomized) will also be available to the IDMC. The Z-Statistic

boundaries (for efficacy and/or futility) in these sensitivity analyses will be consistent with the primary analysis and presented for reference (i.e., should not be used as formal hypothesis testing).

Conditional power will be calculated based on the observed data at the time of the IA for each study individually and will be provided purely for additional information to facilitate the decision around stopping for futility. It will not be used to facilitate any decision on stopping for success.

Additional details on IA designs, microbiological data criteria, stopping boundaries, content and structure of the data output for IA are described in the IDMC charter and a separate IA analysis plan.

3.2. Final Analyses

The final planned primary analyses will be performed after the completion of the following sequential steps:

1. All participants have completed the study as defined in the protocol at the FU Visit.
2. If the study is stopped for success at the IA, primary inferential analysis and a small set of supporting analyses will be repeated on the complete data for participants included in the IA to ensure consistency. Data collected after the IA data cut are considered overrun. Overrun participants will be pooled with the IA participants for all analyses defined in this document except the primary inferential analysis. If the study is not stopped for success, all analyses will be performed on all participant data after study completion.
3. All protocol deviations captured and categorized, and analysis populations defined.
4. All final database cleaning and data lock activities completed by data management.
5. All criteria for the unblinding of subject randomization codes have been achieved.
6. All randomization codes have been distributed per standard operating procedures.

4. ANALYSIS POPULATIONS

Population	Definition / Criteria	Analyses Evaluated
Screened Population	
 All participants who were screened for eligibility Participants will be analyzed according to their randomized study treatment. 	
 Study Population
Intent-to-Treat (ITT) Population	
 All participants randomly assigned to study treatment. Participants will be analyzed according to their randomized study treatment. 	
 Study Population Efficacy
Microbiological ITT (micro-ITT) Population	
 All participants randomly assigned to study treatment who receive at least 1 dose of study treatment and have a qualifying baseline uropathogen from a quantitative bacteriological culture of a pretreatment clean-catch midstream urine specimen. Participants will be analyzed according to their randomized study treatment. 	
 Study Population Efficacy
micro-ITT NTF-S Population	
 All participants in the micro-ITT Population whose baseline qualifying uropathogens are all susceptible to nitrofurantoin (NTF-S)¹. Participants with missing MIC susceptibility results for any qualifying uropathogens will not be included in the NTF-S sub-Population. Participants will be analyzed according to their randomized study treatment. 	
 Study Population Efficacy (including the primary efficacy analysis if the study does not stop for efficacy)
micro-ITT NTF-S (IA Set) Population	
 All participants in the micro-ITT NTF-S Population who, per the interim analysis data, had: 
 the opportunity to reach their Test of Cure (TOC) visit, or had not yet reached their TOC visit, but were already known to be failures (e.g., subjects who took other systemic antimicrobial or withdrew from the study before the TOC visit) Participants will be analyzed according to their randomized study treatment. 
Note: this population will only be used as the primary analysis population if the study stops for efficacy.²
	
 Study Population Efficacy (including the primary efficacy analysis if the study stops for efficacy)
micro-ITT NTF-NS Population	
 All participants in the micro-ITT Population who have any baseline qualifying uropathogens that are NTF-NS, defined as resistant to nitrofurantoin (NTF-R), or intermediate to nitrofurantoin (NTF-I), or no interpretation to nitrofurantoin (NTF-NI), Participants missing MIC susceptibility results for all qualifying 	
 Study Population Efficacy

Population	Definition / Criteria	Analyses Evaluated
	
uropathogens will not be included in the NTF-NS sub-Population.
 
 Participants will be analyzed according to their randomized study treatment. 	

Microbiologically Evaluable at OT (ME-OT) Population
	
 Participants who meet the definition of the micro-ITT Population, follow important components of the study (i.e., (1) receive at least 80% of planned doses as randomized and actual treatment received is the same as randomized, (2) have an interpretable quantitative urine culture at the OT Visit and evaluable clinical scores at the baseline and the OT Visit, (3) have not taken any other systemic antimicrobial before OT unless it was taken for the current infection (therapeutic failure), and (4) have no other major protocol deviation that prevents evaluation of efficacy. Participants will be analyzed according to their randomized study treatment, however, by definition, for all participants in this analysis population the actual treatment received is the same as randomized. 	
 Efficacy

Microbiologically Evaluable at TOC (ME-TOC) Population
	
 Participants who meet the definition of the micro-ITT Population, follow important components of the study (i.e., (1) receive at least 80% of planned doses as randomized and actual treatment received is the same as randomized, (2) have an interpretable quantitative urine culture at the TOC Visit and evaluable clinical scores at the baseline and the TOC Visit, (3) have not taken any other systemic antimicrobial before TOC unless it was taken for the current infection, and (4) have no other major protocol deviation that prevents evaluation of efficacy. Participants will be analyzed according to their randomized study treatment, however, by definition, for all participants in this analysis population the actual treatment received is the same as randomized. 	
 Efficacy

Microbiologically Evaluable at FU (ME-FU) Population
	
 Participants who meet the definition of the micro-ITT Population, follow important components of the study (i.e., (1) receive at least 80% of planned doses as randomized and actual treatment received is the same as randomized, (2) have an interpretable quantitative urine culture at FU Visit (unless microbiological outcome at TOC is persistence or recurrence) and evaluable clinical scores at the baseline and the FU Visit (unless clinical outcome at TOC is clinical improvement or worsening), (3) have not taken any other systemic antimicrobial 	
 Efficacy

Population	Definition / Criteria	Analyses Evaluated
	
before FU unless it was taken for the current infection (therapeutic failure), and (4) have no other major protocol deviation that prevents evaluation of efficacy.
 
 Participants will be analyzed according to their randomized study treatment, however, by definition, for all participants in this analysis population the actual treatment received is the same as randomized. 	
ME-OT NTF-S Population	
 All participants in the ME-OT Population whose baseline qualifying uropathogens are all susceptible to nitrofurantoin. Participants will be analyzed according to their randomized study treatment, however, by definition, for all participants in this analysis population the actual treatment received is the same as randomized. 	
 Efficacy
ME-OT NTF-NS Population	
 All participants in the ME-OT Population who have any baseline qualifying uropathogens that are NTF-NS. Participants will be analyzed according to their randomized study treatment, however, by definition, for all participants in this analysis population the actual treatment received is the same as randomized. 	
 Efficacy
ME-TOC NTF-S Population	
 All participants in the ME-TOC Population whose baseline qualifying uropathogens are all susceptible to nitrofurantoin. Participants will be analyzed according to their randomized study treatment, however, by definition, for all participants in this analysis population the actual treatment received is the same as randomized. 	
 Efficacy
ME-TOC NTF-NS Population	
 All participants in the ME-TOC Population who have any baseline qualifying uropathogens that are NTF-NS. Participants will be analyzed according to their randomized study treatment, however, by definition, for all participants in this analysis population the actual treatment received is the same as randomized. 	
 Efficacy
ME-FU NTF-S Population	
 All participants in the ME-FU Population whose baseline qualifying uropathogens are all susceptible to nitrofurantoin. Participants will be analyzed according to their randomized study treatment, however, by definition, for all participants in this analysis population the actual treatment received is the same as randomized. 	
 Efficacy

Population	Definition / Criteria	Analyses Evaluated
ME-FU NTF-NS Population	
 • All participants in the ME-FU Population who have any baseline qualifying uropathogens that are NTF-NS. • Participants will be analyzed according to their randomized study treatment, however, by definition, for all participants in this analysis population the actual treatment received is the same as randomized. 	
 • Efficacy
Clinically Evaluable at OT (CE-OT) Population	
 • All participants in the ITT Population who follow important components of the study as specified in the protocol (i.e., (1) receive at least 80% of planned doses as randomized and actual treatment received is the same as randomized, (2) have evaluable clinical scores of signs and symptoms at the baseline and the OT Visit, (3) have not received other systemic antimicrobials before OT unless it was for the current infection (therapeutic failure), and (4) have no other major protocol deviation that prevents evaluation of efficacy). • Participants will be analyzed according to their randomized study treatment, however, by definition, for all participants in this analysis population the actual treatment received is the same as randomized. 	
 • Efficacy
Clinically Evaluable at TOC (CE-TOC) Population	
 • All participants in the ITT Population who follow important components of the study as specified in the protocol (i.e., (1) receive at least 80% of planned doses as randomized and actual treatment received is the same as randomized, (2) have evaluable clinical scores of signs and symptoms at the baseline and the TOC Visits, (3) have not received other systemic antimicrobials before TOC unless it was for the current infection (therapeutic failure), and (4) have no other major protocol deviation that prevents evaluation of efficacy. • Participants will be analyzed according to their randomized study treatment, however, by definition, for all participants in this analysis population the actual treatment received is the same as randomized. 	
 • Study Population • Efficacy
Clinically Evaluable at FU (CE-FU) Population	
 • All participants in the ITT Population who follow important components of the study as specified in the protocol (i.e., (1) receive at least 80% of planned doses as randomized and actual treatment received is the same as randomized, (2) have evaluable clinical scores of signs and symptoms at the baseline and the FU Visit (unless clinical outcome at TOC is clinical 	
 • Efficacy

Population	Definition / Criteria	Analyses Evaluated
	improvement or worsening), (3) have not received other systemic antimicrobials before FU unless it was for the current infection (therapeutic failure), and (4) have no other major protocol deviation that prevents evaluation of efficacy). 
 • Participants will be analyzed according to their randomized study treatment, however, by definition, for all participants in this analysis population the actual treatment received is the same as randomized. 	
Safety Population	
 • All randomized participants who receive at least 1 dose of study treatment. • Participants will be analyzed according to their actual treatment received. Note: if a participant receives both gepotidacin and nitrofurantoin they will be summarized within gepotidacin 1500 mg BID.	
 • Safety

1. Broth microdilution nitrofurantoin MIC result from JMI Laboratories (if available) will take precedence over global central laboratory (GCL) nitrofurantoin MIC result for determining susceptibility to nitrofurantoin.
2. The micro-ITT NTF-S (IA Set) Population will include participants who have completed their TOC Visit or had the opportunity to reach their TOC visit (determined by the last day of the TOC visit analysis window per [Table 5](#)) as of the IA data cut-off. Participants who have not had the opportunity to reach their TOC Visit but are known failures (per the SDTM datasets used in the interim analyses) will be in scope of the IA Set if they are randomized prior to the IA data cut-off.

Notes:

- Refer to [Appendix 9](#).
- Qualifying uropathogens specified in any study populations above include only the uropathogen species/groups [Gram-negative bacilli (e.g. *E. coli*, *K. pneumoniae*, *P. mirabilis*), *S. saprophyticus*, and *Enterococcus* spp.], as described in Section [7.3.2](#).
- Evaluable clinical score means non-missing clinical score.
- Significant deviations which prevent evaluation of efficacy and result in exclusion from CE/ME analysis populations will be determined by the study team throughout the conduct of the study before database lock

The term “CE Population” is used to refer to all CE Populations. The term “ME Population” is used to refer to all ME Populations.

Inclusion into the ITT and Safety Population will be determined programmatically from eCRF data.

Inclusion criteria for the micro-ITT/NTF-S/NTF-NS, ME Populations, and CE Populations will be determined programmatically and through manual review conducted by the Sponsor. The Sponsor will be blinded to treatment assignment and may review the data concurrent with conduct of the study. Final determination of population inclusion will be performed after database lock and prior to unblinding. Exclusion from ME/CE

Populations related to receipt of incorrect study drug will be determined programmatically after unblinding.

Nitrofurantoin susceptibility interpretations will be based on the Clinical and Laboratory Standards Institute (CLSI) guidelines to determine participant inclusion into the NTF-S/NTF-NS subpopulations except as described in Section 7.1.6.3.

If the study stops for efficacy the primary analysis population will be the micro-ITT NTF-S (IA Set) Population, and the micro-ITT NTF-S Population (complete trial data including participants included in the IA and overrun participants) will be used for sensitivity analyses (as described in Section 7.1.6.2) to provide a nominal estimate of the treatment difference and 95% CI. If the study does not stop for efficacy the primary analysis population will be the micro-ITT NTF-S Population (complete trial data).

In the event that one or more investigators/sites have had a corrective and preventative action (CAPA) put in place requiring that a supplementary analysis excluding data from these sites be performed, a supplementary analysis will be performed. A flag will be included to identify subjects enrolled by those investigators/sites. This will enable further subpopulations to be defined for the primary analysis populations (micro-ITT NTF-S if the study continues / micro-ITT NTF-S (IA Set) if the study stops for futility). The subpopulation will consist of all subjects in the primary analysis population except subjects from those investigative sites (e.g., micro-ITT NTF-S (CAPA)/ micro-ITT NTF-S (IA Set) (CAPA) respectively) and will be used to perform the additional supplemental analysis for the primary efficacy endpoint only. Note: this analysis is included in the IA recommendation framework per Section 5.5.

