9.2. Sample Size Determination

9.2.1. Justification of Sample Size

Participants will be randomized to gepotidacin and nitrofurantoin in a 1:1 ratio. Assuming a 76% therapeutic success rate for both nitrofurantoin and gepotidacin, a sample size of approximately 884 participants in the micro-ITT NTF-S Population is required, for a design with 1 IA allowing for stopping the study based on efficacy or futility, to provide approximately 90% power to demonstrate noninferiority in the therapeutic response rate of gepotidacin to nitrofurantoin with a 0.025 one-sided alpha level and a -10.0% noninferiority margin. The minimal response rate difference that would meet the statistical criterion for noninferiority is provided in [Table 12](#).

Table 12 Minimal Response Rate Difference for Efficacy and Futility Interim Analysis

Design	Information Fraction	Micro-ITT NTF-S Sample Size	Minimal Response Rate Difference for Noninferiority
Analysis for Efficacy and Futility	60%	530	-2.2%
	100%	884	-3.6%

Micro-ITT NTF-S=Microbiological Intent-to-Treat Nitrofurantoin-Susceptible.

In case a futility-only IA is conducted, under the same assumption for response rate, significance level, and noninferiority margin, a sample size of 768 participants in the micro-ITT NTF-S Population will provide approximately 88% power to demonstrate noninferiority. The minimal response rate difference that would meet the statistical criterion for noninferiority is -4.0% for the final analysis.

The study is planned to enroll approximately 2500 participants to ensure a sufficient number of participants in the primary analysis population (i.e., micro-ITT NTF-S Population). If the study proceeds to an efficacy and futility IA, the maximum target sample size (assuming there is a decision to continue the study at the IA) for the primary analysis population will be around 884 participants. If the study proceeds to the futility-only IA, the maximum target sample size (assuming a decision to continue the study at the IA) for the primary analysis population will be approximately 768 participants. The final number of randomized participants may vary based on the evaluability rate and review of qualifying uropathogens by an unblinded SDAC.

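### Before TOC, only known failures (and early TOC completers) enter the interim analysis set, so membership depends on outcome; the bias is probably below half a point, but a calendar rule removes it almost for free

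*SAP*

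**What the plan says.** SAP Section 3.1 puts into the interim data those who had the opportunity to reach TOC, and also "participants who have not yet reached their TOC visit, but are already known to be failures". The IA Set row in SAP Section 4 repeats the rule: participants who "had not yet reached their TOC visit, but were already known to be failures". The examples given are taking another systemic antimicrobial and withdrawing from the study before TOC. Footnote 2 to that table says "Participants who have not had the opportunity to reach their TOC Visit but are known failures" are in scope if randomised before the cut-off. Footnote 2 alone also admits anyone who has already completed TOC. Otherwise, opportunity is judged by the last day of the TOC analysis window, Day 16 in SAP Table 5.

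On use, SAP Section 4 states: "If the study stops for efficacy the primary analysis population will be the micro-ITT NTF-S (IA Set) Population". Section 7.1.6.1 repeats this. Section 3.2 repeats the primary inference on participants who were in the interim analysis and treats later data as overrun. Section 3.1 derives the actual boundaries from the information fraction in the IA Set.

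**The concern.** Take two participants randomised on the same day, both short of TOC at the cut-off. One has withdrawn and enters as a failure. The other is well and stays out. If she later succeeds, she is overrun and never enters the primary inference after an efficacy stop. The success rates are then not those of any randomised cohort. If early failures accrue faster in one arm, the difference and its Z statistic shift.

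Footnote 2 adds a selection that works the other way. In-window completers are in, while in-window non-attenders wait, although a TOC visit that never happens counts as failure (Protocol Section 9.4.2). This raises success rates and may partly offset the first effect, but nothing ensures that it does.

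At stake are the interim efficacy decision, the futility guidance and, after an efficacy stop, the confirmatory estimate.

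**Working it through.** **Inputs from the documents.** Protocol Section 9.2.1: "Assuming a 76% therapeutic success rate for both nitrofurantoin and gepotidacin", "with a 0.025 one-sided alpha level and a -10.0% noninferiority margin" and "Participants will be randomized to gepotidacin and nitrofurantoin in a 1:1 ratio". SAP Table 2: interim at 530 (265 per arm), boundary Z > 2.104, cumulative alpha 0.018; final at 884, Z > 2.23.

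**The plan's own figures reproduce.**
- Pocock-type spending: 0.025 × ln(1 + (e − 1) × 0.6) = 0.0177, so Z = 2.103. The bivariate-normal solution for the final boundary is 2.23.
- SE at 76/76, 265 per arm: √(2 × 0.76 × 0.24 / 265) = 3.71 points. Minimal difference: −10 + 2.104 × 3.71 = −2.19 (stated −2.2).
- SE at 442 per arm: 2.87 points. Minimal difference: −10 + 2.23 × 2.87 = −3.6 (stated −3.6).
- Power including the futility bound is 90.2%, against a stated "approximately 90% power to demonstrate noninferiority in the therapeutic response rate of gepotidacin to nitrofurantoin".

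**Assumptions, because the documents give no figures.** With 1 to 5 evaluable participants randomised per day and about 12 open days (12 is the TOC target day in SAP Table 5), 12 to 60 participants are open, or 6 to 30 per arm. Of these, 3% to 8% are already known failures.

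**Formulas.** With 265 matured participants per arm, true rate p and k = (open participants per arm) × (early-failure share), the expected rate is 265p / (265 + k). The difference D is gepotidacin minus nitrofurantoin. P(cross) = Φ((D + 0.10)/SE − 2.104), with SE recomputed from the shifted rates and sizes. Without the rule, equality gives Φ(10/3.71 − 2.104) = 0.723, and the null (66% vs 76%) gives Φ(−2.104) = 0.0177.

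**Worked case:** 30 open per arm, 3% early failures on gepotidacin and 8% on nitrofurantoin, so k = 0.9 and 2.4.
- Equality: 201.4/265.9 = 75.74% and 201.4/267.4 = 75.32%, so D = +0.42 points.
- Null: 174.9/265.9 = 65.78% and 75.32%, so D = −9.54, a shift of +0.46.

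| Open per arm | Early failures, gepotidacin / nitrofurantoin | Shift at 76/76 | P(cross) | Shift at 66/76 | P(cross) |
|---|---|---|---|---|---|
| any | rule absent | 0 | 0.723 | 0 | 0.0177 |
| 30 | 3% / 8% | +0.42 | 0.757 | +0.46 | 0.0235 |
| 30 | 8% / 3% | −0.42 | 0.680 | −0.34 | 0.0143 |
| 30 | 8% / 8% | 0 | 0.718 | +0.09 | 0.0187 |
| 6 | 3% / 8% | +0.09 | 0.730 | +0.09 | 0.0187 |
| 6 | 8% / 3% | −0.09 | 0.714 | −0.07 | 0.0169 |

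Averaging over binomial early-failure counts changes little: 0.0233 in place of 0.0235, and 0.719 in place of 0.718. The largest fall in one arm's success rate at 76% is 76.0 − 75.3 = 0.7 points.

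**Beyond these assumptions.** With 40 open per arm, 5% vs 10% gives +0.64 points and 0.0261 at the null; 2% vs 10% gives +0.93 and 0.0309. The effect grows with accrual at the cut-off and with imbalance between arms.

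These figures cover the known-failure clause only. The documents do not allow the opposing early-completer effect to be sized.

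**The case against.** The best defence is that the effect is small and that the SAP has a check on it. After an efficacy stop, SAP Section 7.1.6.2 (sensitivity analysis 1) runs the stratified analysis on the complete micro-ITT NTF-S population, overrun included. That would reveal a distortion. It is nominal, however, and neither replaces the primary inference nor undoes the stop. An efficacy stop also requires the population excluding CAPA sites to cross the boundary (SAP Sections 2.4 and 5.5), so where such exclusions apply the crossing probabilities above overstate the chance of stopping. If the trial continues, the final analysis uses all participants and has no such selection. These points limit the consequences but leave the definition as it is.

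Three stronger readings are tempting.

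- **Serious error inflation.** Put four extra failures on one arm and none on the other. On gepotidacin, at equality, the shift is 201.4/269 − 0.76 = −1.13 points and P(cross) falls to about 0.61. On nitrofurantoin, at the null, P(cross) rises to about 0.035. These are conditional on one extreme split and are not error rates. Four of 30 against none is 13% vs 0%, outside the assumed range. With 8% in both arms, a net excess of four or more on nitrofurantoin has probability of about 5%.
- **Bias in favour of gepotidacin.** The documents do not support a direction. Protocol Section 2.3.1 lists gastrointestinal events among the commonest with gepotidacin, and also 8% nausea with nitrofurantoin. Stopping treatment alone is not failure under the treatment-policy strategy; withdrawal or another antimicrobial is needed. More early failures on gepotidacin would be conservative for noninferiority, would cost power and would push towards futility.
- **Departure from the protocol.** Protocol Sections 9.1 and 9.5 time the interim on participants who have achieved TOC and do not mention adding early failures; SAP Section 2.1 does not list the addition. But that text sets timing and does not define the set, so this is a gap and not a contradiction.

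**Conclusion.** The definition selects on outcome and attendance, and that set governs the interim tests and the primary analysis after an efficacy stop. With up to 30 open participants per arm and 3% to 8% early failures, the difference moves by less than half a point in either direction against a 10-point margin. Interim type I error lies between about 0.014 and 0.023 in place of 0.018, and P(crossing) at equality between about 0.68 and 0.76 in place of 0.72. With equal early-failure rates the effect is negligible.

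This is a moderate flaw that should be fixed, and it does not by itself undermine the design. The size rests wholly on assumed accrual and early-failure rates, so the sponsor cannot show in advance from these documents that it is negligible.

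**What to change.** Before interim unblinding, define the IA Set by calendar only: all micro-ITT NTF-S participants whose study Day 16 falls on or before the IA data cut-off, whatever their status. Delete the known-failure clause in SAP Section 3.1, the IA Set row of Section 4 and footnote 2. Delete the completed-TOC clause, which stands only in footnote 2. Treat everyone else as overrun, count the approximately 530 on this set, and carry the wording into the IDMC analysis plan. Early failures outside the set can be reported separately.

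With membership set by date, the known-failure shift disappears and the crossing probabilities return to 0.723 and 0.0177. The cost is wording. Typically 1 to 6 early failures move to overrun (at most 14 in the scenarios simulated), as do TOC completers whose Day 16 has not passed. Since TOC is due on Days 10 to 13, the cut-off may move by some 3 to 6 days (16 − 13 to 16 − 10). No trial procedure changes.
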